# 8.4 Secondary endpoints

There are two secondary endpoints: (i) Day 14 overall survival and (ii) Day 14 ventilator-free survival, both of which are binary endpoints. Day 14 overall survival will be summarized by the proportion of the twelve patients who are alive at Day 14 after starting treatment, and Day 14 ventilator-free survival will be summarized by the proportion of the twelve patients who are both alive and not using a ventilator at Day 14 after starting treatment. Both proportions will be accompanied by an exact 95% confidence interval.

We will also continually monitor the study for excessive Day 14 mortality. In parallel with our decision rule related to excessive severe hemorrhagic events, we will suspend accrual if we see if we see at least five deaths by Day 14 among the first six patients, or at least seven deaths by Day 14 among the first eleven patients. If the true Day 14 mortality rate is 70% (which is the historical rate for patients with respiratory comprise), the study has a probability of 0.80 of being suspended. Conversely, if the Day 14 mortality rate is 50%, the study has a much lower probability of 0.30 of being suspended.

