# 1.0 STUDY SYNOPSIS

This is an investigator initiated, open label trial of defibrotide for therapy of patients with SARS-CoV2 related acute respiratory distress syndrome (ARDS). The primary endpoint is safety and tolerability. Secondary endpoints will assess response and ventilator free survival.

*Eligibility*: Patients ≥ 18 years in age with evidence of SARS-CoV2 related ARDS. All patients must exhibit signs of coagulopathy evidenced by a D-dimer > 2X ULN.

**Study therapy:** Defibrotide will be administered intravenously (IV) every 6 hours (Q6H) for 7 days of therapy. Patients who meet defined toxicity and/or efficacy criteria within the 7-day period may cease study therapy at that earlier time point. Patients with a partial response to study therapy by day 7 (defined as > 20% decrease in supplemental oxygen) may continue to receive an additional 7 days of therapy (14 days total therapy). Toxicity (including rate of hemorrhage / bleeding) will be assessed. Each patient will be monitored for 14 days, including 7 days of therapy and 7 days of post-therapy observation.

**Sample Size:** 12 patients. An interim assessment for toxicity and early mortality will be performed after the first six patients have enrolled. Accrual may proceed to a maximum of 12 patients, if the stopping rules are not met within the first six patients.

**Other:** The study will target patients with either early or late-phase ARDS, provided patients have not required mechanical ventilation for > 7 consecutive days. The study allows co-enrollment with other SARS-CoV2 therapy trials, provided those trials are not also utilizing other anti-coagulant or fibrinolytic agents.

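### The Day 14 mortality rule in section 8.4 prints no trigger for a sixth death, so 6 deaths in 8 patients leaves accrual open while 7 in 11 suspends it

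*Combined protocol and SAP*

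**What the plan says.** Section 8.4 introduces the rule with "We will also continually monitor the study for excessive Day 14 mortality" and ties it to the bleeding rule: "In parallel with our decision rule related to excessive severe hemorrhagic events, we will suspend accrual". Two triggers follow: "at least five deaths by Day 14 among the first six patients, or at least seven deaths by Day 14 among the first eleven patients". At 70% mortality, which the plan takes as the historical rate, "the study has a probability of 0.80 of being suspended". For the favourable case, "if the Day 14 mortality rate is 50%, the study has a much lower probability of 0.30 of being suspended". The synopsis (section 1.0) caps enrolment: "Accrual may proceed to a maximum of 12 patients".

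No prior, mortality threshold or posterior cut-off is given for this rule. Section 8.3 gives all three for bleeding: a Beta(2,8) prior, a threshold of 0.20 and a cut-off of 80%. Its printed triggers are three events by patient 6 and four by patient 11, which are consecutive counts.

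**The concern.** Under continual monitoring, every death count between the first and last trigger needs a latest patient number at which it suspends accrual. The bleeding rule steps from three to four, so nothing is skipped between its two triggers. The mortality rule steps from five to seven and gives the sixth death no limit.

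Whoever applies the text literally would find no trigger met at 6 deaths in 8 patients (75%) or 6 in 9 (67%), yet would suspend at 7 in 11 (64%). At stake is the timing of a safety pause for deaths in a trial of at most 12 patients.

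**Working it through.** **Inputs.** Triggers of 5 deaths by patient 6 and 7 by patient 11; mortality p = 0.70 and 0.50, with stated suspension probabilities 0.80 and 0.30 (all from 8.4); at most 12 patients (1.0). The rate p = 0.60 is added as an intermediate case. Patients are treated as independent, with each outcome known before the next look.

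**1. The plan's own figures.** Let X6 be deaths in the first six patients and Y deaths in patients 7 to 11.

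P(suspend) = P(X6 ≥ 5) + Σ P(X6 = k) · P(Y ≥ 7 − k), for k = 2, 3, 4.

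- p = 0.50: 7/64 + (15·1 + 20·6 + 15·16)/2048 = 0.1094 + 0.1831 = **0.2925** (stated 0.30).
- p = 0.70: 0.4202 + 0.0595·0.1681 + 0.1852·0.5282 + 0.3241·0.8369 = 0.4202 + 0.3791 = **0.7993** (stated 0.80).

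Both agree to within 0.01. The same calculation on the printed bleeding counts gives 0.188, 0.462 and 0.725 against the stated 0.19, 0.47 and 0.73, so the plan's figures are loose by a similar amount there.

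**2. The uncovered path.** Reaching 6 of 8 without having met 5 of 6 requires exactly four deaths in the first six and then deaths of patients 7 and 8:

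P(path) = 15 p⁴(1 − p)² · p² = 15 p⁶(1 − p)².

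- p = 0.70: 15 · 0.1176 · 0.09 = **0.159**
- p = 0.60: 15 · 0.04666 · 0.16 = **0.112**
- p = 0.50: 15/256 = **0.059**

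**3. What happens next on that path.** A seventh death in patients 9, 10 or 11 suspends accrual, one to three patients later. With probability (1 − p)³ none occurs and accrual is never suspended. Suspension missed altogether is therefore 0.159 · 0.027 = 0.004 at 70% and 0.059 · 0.125 = 0.007 at 50%.

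**4. Effect of adding a six-death trigger** (exact patient-by-patient recursion):

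| Rule | P(suspend), 50% | P(suspend), 70% | Mean accrual at suspension, 50% | Mean accrual at suspension, 70% |
|---|---|---|---|---|
| As printed | 0.2925 | 0.7993 | 8.61 | 7.70 |
| Plus 6 by patient 8 | 0.2998 | 0.8036 | 8.32 | 7.45 |
| Plus 6 by patient 9 | 0.3242 | 0.8179 | 8.07 | 7.25 |

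**5. Is 6 of 8 stronger evidence than 7 of 11?** Take the likelihood ratio of the plan's two rates, 0.70 against 0.50: 1.4^deaths · 0.6^survivors.

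- 6 of 8: 1.4⁶ · 0.6² = 2.71
- 7 of 11: 1.4⁷ · 0.6⁴ = 1.37

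Going from 6 of 8 to 7 of 11 adds one death and two survivors, which multiplies the ratio by 1.4 · 0.36 = 0.50.

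**6. Would a posterior rule skip the sixth death?** I searched Beta priors (total weight 1 to 20, mean 0.1 to 0.9), thresholds 0.30 to 0.75 and cut-offs 0.50 to 0.99 for rules whose five-death limit is patient 6 and whose seven-death limit is patient 11. There were 261. All suspend at six deaths, with the limit at patient 8 in 131 and at patient 9 in 130. None skips it. The search shows that a limit should exist, but not which one.

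**The case against.** **The 0.30 looks wrong.** A reader might infer that it was computed for a different rule, because the printed counts give 0.2925 and adding 6 by 8 gives 0.2998. The documents do not support that. The gap is 0.75 points, and the bleeding figures show a similar one (0.462 against 0.47). Other additions fit as well: adding 4 of 4 to the printed counts also gives 0.300. The match is compatible with an omitted clause but does not prove one.

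**A higher rate is tolerated than a later one that suspends.** This is not an error in itself. The bleeding rule does the same: 3 of 7 (43%) does not suspend and 4 of 11 (36%) does, and this is coherent, with posterior probabilities of 0.798 and 0.804 against the 0.80 cut-off. The defect here is the missing count. Adding 6 by 8 would still leave 6 of 9 below the boundary, which is acceptable if the stated prior and cut-off place it there.

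**Other safeguards exist.** Section 11 holds enrolment for a DSMB review once patient 6 has completed therapy, the protocol monitoring committee meets monthly, and extra DSMB meetings are possible. Deaths are serious adverse events reported to the principal investigator within 24 hours (10.3, 10.7). So it would be too strong to say that enrolment would run on unchecked. But on this path the study stands at 4 of 6 at the DSMB review, so the mortality trigger is not met, and any later pause rests on judgement.

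**The effect is small.** This stands. Most such paths suspend anyway, and the rule is secondary to the hemorrhage endpoint.

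**Conclusion.** The printed mortality boundary is incomplete for a rule described as continual and parallel to the bleeding rule. Four deaths in the first six patients followed by two more meets no written trigger. The chance of this is about one in six at the plan's historical rate of 70% (0.159) and 0.059 at 50%. The practical consequence is modest: suspension delayed by one to three patients on that path, and 0.4 to 0.7 points of suspension probability overall. It is worth correcting because the text governs a safety pause, but it does not undermine the design, and the stated 0.80 and 0.30 can stand.

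This rests on independent outcomes known before each look. The claim that a six-death limit belongs in the rule also assumes a posterior-probability rule like that in 8.3, since 8.4 does not state its basis.

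**What to change.** In 8.4, add the six-death trigger between the two printed ones, and state the prior, mortality threshold and posterior cut-off from which the boundary is derived, as 8.3 does.

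- If the limit is six deaths among the first eight patients, keep 0.80 and 0.30 (0.804 and 0.300).
- If the underlying rule puts it at patient 9, restate them as 0.82 and 0.32.

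The cost is one clause and one sentence of derivation. With 6 by 8, the chance of an accrual pause rises by 0.7 points at 50% mortality and 0.4 at 70%. In return, mean accrual at suspension falls from 7.70 to 7.45 at 70% and from 8.61 to 8.32 at 50%.

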# 8.3 Primary stopping rule

An incidence of > 20% hemorrhagic complications would be unacceptable in this setting. Thus, we will continually monitor the observed proportion of patients with major bleeding complications. We start with prior Beta(2,8) distribution, which has mean 0.2. If ever we have more than 80% posterior probability that the true proportion is greater than 0.20,

accrual to the protocol will be suspended to allow the DSMB to review the incidence of major bleeding.

Specifically, if we see at least **three** patients with major bleeding among the first six patients, or at least **four** patients with major bleeding among the first eleven patients, the study will be suspended. If the true proportion of major bleeding events is 0.20, the study has a probability of 0.19 of being suspended. If the true proportion of major bleeding events is 0.30 or 0.40, the probability of trial suspension is 0.47 and 0.73, respectively. Note that if the trial is suspended to accrual, the accrual is expected to be seven patients.

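### Does the Day 14 mortality rule in section 8.4 fail its purpose because it usually suspends at the 70% historical rate?

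*Combined protocol and SAP*

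**What the plan says.** Section 8.4 introduces the rule with "We will also continually monitor the study for excessive Day 14 mortality" and links it to the bleeding rule: "In parallel with our decision rule related to excessive severe hemorrhagic events". Accrual is suspended at five or more deaths among the first six patients, or at "at least seven deaths by Day 14 among the first eleven patients". Two operating points are printed. The first begins "If the true Day 14 mortality rate is 70% (which is the historical rate for patients with respiratory comprise") and gives 0.80. The second reads "Conversely, if the Day 14 mortality rate is 50%, the study has a much lower probability of 0.30 of being suspended". No mortality rate is named as unacceptable, and no prior or posterior threshold is given for this rule.

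Section 8.3 is more explicit about bleeding. It states a limit, "An incidence of > 20% hemorrhagic complications would be unacceptable in this setting", a Beta(2,8) prior and an 80% posterior threshold. It adds: "If the true proportion of major bleeding events is 0.20, the study has a probability of 0.19 of being suspended". Its consequence is a pause: "accrual to the protocol will be suspended to allow the DSMB to review the incidence of major bleeding".

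Section 11.0 separately holds enrollment once the sixth patient has finished study drug, so that the DSMB can decide whether the trial continues.

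**The concern.** Read quickly, section 8.4 sets 70% as the norm and promises to detect an excess over it. On that reading the rule performs badly. It suspends with probability 0.80 when mortality only equals the norm, and 0.55 when it is ten points better. The second boundary, 7/11 = 64%, lies below 70%, so a trial could be paused for excessive mortality with an observed rate under the historical one.

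The link to section 8.3 sharpens this. There, suspension at the named reference rate is infrequent (0.19); here, at the named historical rate, it is the usual outcome (0.80). The same adjective appears to cover two opposite calibrations.

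At stake is what the DSMB could infer from a pause. A pause is only slightly more likely at 80% mortality than at 70%, so it says little about harm beyond history. A board that took the wording at face value might read lack of improvement as evidence of harm.

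**Working it through.** **Inputs.** Boundaries 5/6 and 7/11, and stated probabilities 0.80 and 0.30 (section 8.4). Bleeding boundaries 3/6 and 4/11, Beta(2,8) prior, 80% posterior threshold, stated probabilities 0.19, 0.47 and 0.73 (section 8.3). Patients are taken as independent with Day 14 status known.

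**Step 1: reproduce the printed figures.** With X₆ ~ Bin(6, p) and X₅ ~ Bin(5, p) for the next five patients,

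P(suspend) = P(X₆ ≥ 5) + Σ over k ≤ 4 of P(X₆ = k) · P(X₅ ≥ 7 − k).

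| True Day 14 mortality | First boundary | Added by second | Total | Printed |
|---|---|---|---|---|
| 40% | 0.0410 | 0.0711 | 0.112 | – |
| 50% | 0.1094 | 0.1831 | 0.293 | 0.30 |
| 60% | 0.2333 | 0.3162 | 0.550 | – |
| 70% | 0.4202 | 0.3791 | 0.799 | 0.80 |
| 80% | 0.6554 | 0.2970 | 0.952 | – |
| 90% | 0.8857 | 0.1117 | 0.997 | – |

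Checking after every patient gives the same totals, because cumulative deaths cannot fall. The printed figures are right. The ratios behind the concern also hold: 0.9523/0.7993 = 1.19 for 80% against 70%, and 0.7993/0.2925 = 2.73 for 70% against 50%.

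**Step 2: compare like with like.** The bleeding rule recomputes to 0.188 at 20%, 0.462 at 30% and 0.725 at 40%. Set out by lower and higher rate, 20 points apart:

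| Rule | Lower rate | Higher rate |
|---|---|---|
| Bleeding | 0.19 at 20% | 0.73 at 40% |
| Mortality | 0.29 at 50% | 0.80 at 70% |

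The two rules have the same shape. They look opposed only if the lower point of one is paired with the upper point of the other.

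**Step 3: can the parallel be literal?** Section 8.3 uses a prior of total weight 10 centred on the reference rate, and suspends when the posterior probability of exceeding that rate passes 0.80. For bleeding this gives 0.836 at 3/6 and 0.804 at 4/11, both over the line. The same recipe for mortality with reference rate m uses the prior Beta(10m, 10(1 − m)) and, after k deaths in n, evaluates P(p > m) under Beta(10m + k, 10(1 − m) + n − k).

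| Deaths | m = 40% | m = 45% | m = 50% | Printed rule |
|---|---|---|---|---|
| 4/6 | 0.787 | 0.743 | 0.696 | continue |
| 5/6 | 0.905 | 0.878 | 0.849 | suspend |
| 6/11 | 0.755 | 0.675 | 0.588 | continue |
| 7/11 | 0.873 | 0.816 | 0.748 | suspend |

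References of 40% and 45% both return the printed counts at the two stated looks; 50% does not, since 7/11 falls short of 0.80. At 45% the suspension probability is 0.0692 + 0.1206 = 0.190, the same as for bleeding at 20%. At 40% it is 0.112. These reference rates are inferred; the documents give none.

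**Step 4: test the natural rewording.** One might describe the rule as suspending unless mortality is convincingly below 70%. It does not do that. It continues at 4/6, and P(X₆ ≤ 4) at 70% is 0.58. It continues at 6/11, and P(X₁₁ ≤ 6) at 70% is 0.21. Neither result is convincing evidence of a rate below 70%.

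**Step 5: what would specificity at 70% cost?** A rule of 6/6 or 10/11 suspends with probability 0.1176 + 0.0508 = 0.17 at 70%, but only 0.2621 + 0.1288 = 0.39 at 80%. At this sample size, rarely pausing at 70% means usually missing 80%.

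**The case for a change.** The best case for a change is that the plan should state what its rule is for. Section 8.4 names no limit, shows nothing above 70%, and omits the 0.55 at 60%, which readers may find uncomfortable. Section 11.0 asks the DSMB to decide on termination or continuation, and at 70% mortality the first boundary alone triggers with probability 0.42, so the board should know whether a trigger signals harm or lack of benefit. The 70% carries no source. The background in section 4.0 reports Day 28 mortality of 52.4% with D-dimer above six times the upper limit of normal, approaching 60% above eight times, while entry requires only twice. The wording would be cheap to repair.

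Part of this stands. The reference rate is not stated, and the 70% has neither a source nor a label as an assumption. The populations may differ, so the background figures do not refute it. They do, however, weaken the premise that 70% is the level at which nothing is wrong in this trial.

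The inference that the rule misfires does not stand. The text places 0.80 at 70% against a contrasting, much lower 0.30 at 50%, so the intended direction is visible. The hypothesis in section 2.0 is improved survival, so mortality no better than history can fairly count as too high. A DSMB looking at 7/11 sees 64% and has the 70% in the same paragraph.

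**Conclusion.** No change is needed. The probabilities in section 8.4 are correct. The rule discriminates in the range it was built for (0.29 at 50%, 0.80 at 70%) and still rises to 0.95 at 80% and 0.997 at 90%. Saying it cannot detect excess measures it against a definition, above 70%, that the plan does not give.

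The practical reach is small. Enrollment is held for DSMB review after the sixth patient whatever the count. If 5/6 is not met, at most four deaths have occurred, so the seventh cannot come before patient 9; the second boundary can hold back at most three of the twelve patients. The action is a suspension of accrual, and any error is toward more review.

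What remains is missing detail: the reference rate behind the counts and the origin of the 70%. Supplying either would leave the boundaries, the chance of a pause, the DSMB's review and every trial result as they are. The conclusion assumes independent patients and prompt knowledge of Day 14 status. The 40–45% reference shows only that the stated parallel with the bleeding rule can be literal; it is not evidence of what the authors used.

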# 8.5 Definition of evaluable subjects

Subjects who receive at least one dose of the study drug (defibrotide) would be considered evaluable for the primary and secondary study endpoints. Subjects who die following consent, but prior to initiation of the study therapy (defibrotide), are not evaluable for safety, and will be replaced on study.

# 9.0 OFF STUDY CRITERIA

Defibrotide will be discontinued for any of the following reasons:

- Withdrawal of consent / patient choice.
- The patient experiences an adverse event which, in the opinion of the Investigator, contraindicates continuation in the study.
- Protocol violation, including disallowed concomitant therapy.
- The Investigator considers it not in the patient's best interest to continue.
- Defibrotide-related toxicity (including hemorrhage as defined in section 6.4)
- Subject death.

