# 6.4 Criteria to Hold Study Therapy

Study drug will be held in the following settings:

Patients who develop signs of "major bleeding" as defined by International Society on Thrombosis and Haemostasis (ISTH) criteria (Appendix 3), will have defibrotide held at that time.

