#### Per ISTH criteria:

- The term "major bleeding" is defined as symptomatic bleeding in a critical area or organ, including intracranial, intra-spinal, intraocular, retroperitoneal, intra-articular, pericardial, or intramuscular with compartment syndrome.
- Any bleeding associated with a decline in hemoglobin level of ≥ 2.0 g/dl, leading to transfusion of two or more units of whole blood or red cells will constitute a major bleeding episode, and defibrotide will be held.

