#### Additional criteria:

- In addition, defibrotide therapy will be held if symptomatic alveolar hemorrhage, macroscopic hematuria, uncontrolled menorrhagia (i.e. requiring therapy), uncontrolled epistaxis (> 10 minutes duration) requiring cauterization and/or nasal packing, or uncontrolled bleeding from a wound site (i.e. bleeding requiring therapeutic intervention) occur.
- Blood tinged endotracheal secretions, microscopic hematuria, mild menorrhagia, and/or epistaxis < 10 minutes duration do not require withholding of drug therapy unless the treating medical team deems that the event requires direct medical intervention.

Therapy may resume once the bleeding diathesis has been resolved for at least 24 hours, and may be restarted at the same dose and dosing schedule. If any further signs of bleeding develop upon re-initiation of therapy, defibrotide would be discontinued and not re-started. Patients who develop signs of CNS hemorrhage or diffuse alveolar hemorrhage

should discontinue study therapy immediately, and will not resume therapy at any time point.

Defibrotide will be held for surgical procedures or to accommodate other urgent intervention (central line placement) without necessitating dose modification. For surgical procedures it is recommended that defibrotide administration be completed > 2 hours prior to the procedure. The DF may be resumed 24 hours after completion of the procedure (or later) based upon the clinical discretion of the treating physician.

In situations in which defibrotide therapy was temporarily held and then resumed, no additional doses of defibrotide will be given to account for any doses that were missed while the drug was being held.

Defibrotide will be discontinued permanently for the development of a "severe or life-threatening (anaphylaxis) hypersensitivity reaction.

Defibrotide will be discontinued permanently if a patient initiates extra-corporeal membrane oxygenation (ECMO) therapy for any reason.

Defibrotide dosing for acute hypersensitivity reactions is discussed in section 6.5 below.

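### Section 9.0 discontinues defibrotide for drug-related bleeds that Section 6.4 only holds and lets restart, and Section 6.4 sets no boundary between its hold and no-restart terms for alveolar and intracranial bleeding

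*Combined protocol and SAP*

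**What the plan says.** Section 9.0, headed Off Study Criteria, opens with "Defibrotide will be discontinued for any of the following reasons". One listed reason is "Defibrotide-related toxicity (including hemorrhage as defined in section 6.4"). It mentions neither a hold nor a restart.

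Section 6.4 is titled as criteria to hold therapy and works in three steps.

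- **Hold.** Patients with ISTH major bleeding "will have defibrotide held at that time". Major bleeding covers "symptomatic bleeding in a critical area or organ, including intracranial, intra-spinal, intraocular, retroperitoneal, intra-articular, pericardial, or intramuscular with compartment syndrome". It also covers a hemoglobin decline leading to transfusion, which "will constitute a major bleeding episode, and defibrotide will be held". An additional list begins: "defibrotide therapy will be held if symptomatic alveolar hemorrhage, macroscopic hematuria", and goes on to menorrhagia, epistaxis and wound bleeding, each with a severity qualifier.
- **Restart.** "Therapy may resume once the bleeding diathesis has been resolved for at least 24 hours". Dose and schedule are unchanged. Further bleeding after restart ends therapy for good.
- **No restart.** "Patients who develop signs of CNS hemorrhage or diffuse alveolar hemorrhage" are to stop at once and never resume.

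Section 13.0 also sends the reader to Section 6.0 for holding doses.

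**The concern.** The two sections attach different actions to the same event. A team working from Section 6.4 would pause the drug for, say, macroscopic hematuria judged drug-related, and could restart it. A team working from Section 9.0 would end treatment. Nothing says which section governs.

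Within Section 6.4, alveolar bleeding appears under the hold list with one adjective and under the no-restart sentence with another, and neither term is defined. Intracranial bleeding is in the hold list, while CNS hemorrhage is in the no-restart sentence.

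The primary objective is safety and tolerability, and the primary endpoint in Section 8.1 is bleeding, in at most 12 patients. Whether a patient is given the drug again after a bleed is a patient-safety matter. It also determines how exposure and discontinuation for bleeding will read in the report.

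**Working it through.** The plan gives no figure on this point, so the check is a comparison of text and a count.

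**1. Consequence of a bleed by section**

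| Bleed, judged drug-related | Section 6.4 | Section 9.0 |
|---|---|---|
| Critical-site major bleed outside the CNS | Hold, restart allowed | Discontinue |
| Hemoglobin decline with transfusion | Hold, restart allowed | Discontinue |
| Hematuria, menorrhagia, epistaxis or wound bleed meeting the 6.4 wording | Hold, restart allowed | Discontinue |
| Symptomatic alveolar hemorrhage not called diffuse | Hold, restart allowed | Discontinue |
| CNS or diffuse alveolar hemorrhage | Permanent stop | Discontinue |
| Any further bleeding after restart | Permanent stop | Discontinue |

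The sections agree in the last two rows and differ in the first four.

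**2. How many triggers differ**

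- Critical sites in 6.4: intracranial, intraspinal, intraocular, retroperitoneal, intra-articular, pericardial, intramuscular with compartment syndrome = 7.
- Hemoglobin and transfusion criterion = 1.
- Additional criteria: alveolar, hematuria, menorrhagia, epistaxis, wound = 5.
- Total: 7 + 1 + 5 = 13. Fatal bleeding, listed only in Appendix 3, is left out because restart cannot arise.
- Permanent stop at the first event: intracranial, read as CNS (1); plus intraspinal if that counts as CNS (2); plus symptomatic alveolar if that counts as diffuse (3).
- Restart allowed: 13 − 3 = 10 up to 13 − 1 = 12.

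This counts categories, not patients.

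**3. Role of attribution.** Section 9.0 reaches only defibrotide-related toxicity, and Section 10.4 has the investigator grade causality. The restart rule in 6.4 does not depend on causality. The conflict is therefore confined to drug-related bleeds, but within that group it applies to every trigger that allows restart.

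**4. The overlaps inside 6.4.** A symptomatic, diffuse alveolar bleed meets both the hold item and the no-restart sentence. Section 5.2.2 glosses pulmonary hemorrhage as diffuse alveolar hemorrhage, which does not help to place a symptomatic bleed that is not diffuse. Intracranial bleeding likewise meets both the hold list and the no-restart sentence, and intraspinal bleeding may do so.

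**5. What depends on the choice**

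- Section 7.0: daily pulmonary indices, WHO score, blood counts and coagulation tests run until cessation of drug. Study blood tests end with the last day of drug.
- Section 7.7, note h: adverse events are assessed daily for 7 days after therapy while the patient is in hospital, with a contact 30 days after the last dose.
- Section 10.7: discontinuations for safety events go to the drug supplier within 1 business day.

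Illustration (assumed timing): a bleed on day 3 that ends therapy gives daily assessment to day 3 + 7 = 10 and contact at day 3 + 30 = 33. If the drug restarts and finishes on day 7, these become day 7 + 7 = 14 and day 7 + 30 = 37.

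**6. Primary endpoint.** Section 8.1 asks whether a hemorrhagic complication occurs within 14 days, and Section 8.3 counts patients with major bleeding. A patient whose first major bleed triggers the hold is counted whatever happens next. Repeat bleeds and discontinuation are not endpoints in 8.1 or 8.4. The remaining route is indirect: a non-major hold event, restart, then a major bleed.

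**The case against.** The strongest reply is that Section 9.0 is a one-line summary that defers to Section 6.4. On that reading it means that drug is discontinued when 6.4 says so: on renewed bleeding, CNS hemorrhage or diffuse alveolar hemorrhage. Section 13.0 supports treating Section 6.0 as operative. This is plausible and may be what was meant, but it is not written. Section 9.0 cites hemorrhage as defined in 6.4, not the subset that 6.4 stops permanently.

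It might also be said that discontinued need not mean permanently, since 6.4 adds that word in places. But Section 6.3 uses the bare verb for the end of therapy, Section 6.5 contrasts it with held, and Section 9.0 places it over a list that includes death and withdrawal of consent.

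Several stronger readings are tempting and should not be drawn:

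- **All 6.4 bleeds are in conflict.** They are not; bleeds judged unrelated to defibrotide fall outside this reason in Section 9.0.
- **Section 6.4 flatly contradicts itself on alveolar hemorrhage.** The adjectives differ, and the no-restart sentence follows the restart rule and can be read as an exception to it. What stands is an undefined boundary. The same holds for intracranial bleeding.
- **Follow-up is lost once drug stops.** Section 7.7, note h, and Section 10.2 continue safety collection to 30 days after the last dose. Even in the day-3 illustration this runs past day 14. Only the Off Study heading raises the doubt.

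**Conclusion.** Wrong as written: an internal contradiction between Sections 9.0 and 6.4 for drug-related bleeds, together with two undefined overlaps inside 6.4. By category, 10 to 12 of 13 triggers are open to both consequences when the bleed is judged drug-related. This rests on reading discontinued as different from held, which is how the protocol uses the words elsewhere.

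The effect is on re-exposure after a bleed, on exposure and discontinuation counts, and on assessments tied to cessation or last dose. A reader might infer that the primary endpoint or the stopping rule is compromised. The documents do not support that, because a first major bleed counts either way.

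Nor can the number of affected patients be stated. The 20% in Section 8.3 is a limit of acceptability, not an expected rate, and it includes CNS bleeds, on which the sections agree. The label table in Section 13.0 gives pulmonary alveolar hemorrhage of grade 4-5 in 12 of 176 (7%). That makes the unclear category foreseeable, but the patients were post-transplant and the figure is not split by the two terms in 6.4.

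Because the point concerns giving drug again after the trial's main safety event, it should be corrected even though the analysis is little affected.

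**What to change.** Amend Sections 6.4 and 9.0 together:

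- Give each bleed listed in 6.4 one stated consequence, and word the hemorrhage reason in Section 9.0 to match. Say whether attribution to defibrotide changes that consequence.
- State which alveolar bleeds fall under the hold list and which under the no-restart sentence. Do the same for intracranial and intraspinal bleeding in relation to CNS hemorrhage.
- State that the Off Study Criteria heading refers to stopping drug, and that the follow-up in Section 7.7, note h, and Section 10.2 continues.

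Which bleeds allow restart is a clinical decision for the sponsor and DSMB; this review takes no view on it. The cost is a wording amendment, with no change to sample size, endpoint or stopping rule.
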